To evaluate the effect of dapagliflozin-finerenone combination on albuminuria in patients with chronic kidney disease and type 2 diabetes compared to dapagliflozin alone.

4.2 Specific Objectives:

1. To compare the change in urinary albumin-to-creatinine ratio (UACR) from baseline to the end of the study between dapagliflozin - finerenone combination group and dapagliflozin alone group.
2. To compare the changes in serum potassium levels between the two groups during the study period.
3. To estimate and compare the changes of eGFR between the two groups.
4. To evaluate the proportion of patients achieving a clinically significant reduction in albuminuria (e.g., $\geq 30\%$ decrease in UACR) in each groups.
5. To evaluate the overall safety and tolerability profiles of the combination therapy compared to dapagliflozin monotherapy.

5. Materials and method:

5.1. Type of study: Randomized, open-label, active controlled trial.

5.2 Place of Study: Department of Nephrology, Medicine and Endocrinology & Metabolism, Chittagong Medical College Hospital, Chattogram, Bangladesh.

5.3 Study period: One and half year from acceptance of protocol.

5.4 Study population: Adults with chronic kidney disease and type 2 diabetes attending the Nephrology, Medicine and Endocrinology & Metabolism outdoors at CMCH will be the study population during the study period.

5.5 Study groups: Based on the interventions, there will be two groups in the study

1. Experimental group: Dapagliflozin 10 mg plus finerenone 10 mg
2. Control group : Dapagliflozin 10 mg alone

5.6 Sampling technique: Consecutive patients attending the Nephrology, Medicine and Endocrinology & Metabolism Departments at CMCH will undergo screening based on predefined inclusion and exclusion criteria. Eligible participants will be randomly allocated (via computer-generated randomization) to one of the two treatment arms.

5.7 Inclusion criteria:

- Patients aged ≥ 18 years
- Patients with T2 DM , as defined by the American Diabetic Association.
- Urinary ACR ≥ 30 mg/g and eGFR ≥ 25 ml/min per 1.73 m²
- Prior treatment with ACEIs or ARBs for more than four weeks up to the maximum tolerated dose
- Serum potassium ≤ 4.8 mmol/L

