5.10 List of Variables

Demographic Variables

Variables	Type	Value	Expression
Age	Discrete	In completed years	Mean \pm SD
Sex	Categorical	Male / Female	Frequency (%)
Monthly income	Continuous	In local currency (BDT)	Mean \pm SD /Median (IQR)

Clinical Variables

Variables	Type	Value	Expression
Duration of diabetes	Discrete	In years	Mean \pm SD
Duration of HTN	Discrete	In years	Mean \pm SD
Current medication for DM	Categorical	Insulin/Oral Hypoglycemic Agents/Both	Frequency (%)
Current medication for HTN	Categorical	ACE inhibitor/ARB/MRAs/Beta-blocker/Calcium channel blocker/Diuretics/Others	Frequency (%)
Blood pressure	Continuous	In mm Hg	Mean \pm SD
Height	Continuous	Meter	Mean \pm SD
Weight	Continuous	Kg	Mean \pm SD
BMI	Continuous	kg/m ²	Mean \pm SD
Adverse events	Categorical	Present / Absent	Frequency (%)

Biochemical Variables

Variables		Type	Value	Expression
UACR		Continuous	mg/g	Mean \pm SD
eGFR		Continuous	mL/min/1.73 m ²	Mean \pm SD
Serum creatinine		Continuous	mg/dL	Mean \pm SD
Serum potassium		Continuous	mmol/L	Mean \pm SD
Fasting blood glucose		Continuous	mg/dL	Mean \pm SD
2 hour postprandial blood glucose		Continuous	mg/dL	Mean \pm SD
HbA1C		Continuous	Percent (%)	Mean \pm SD
Urinalysis	Albumin	Categorical	-/trace/+/++/+++/++++	Frequency (%)
	RBC	Discrete /HPF	Mean \pm SD
	WBC	Discrete /HPF	Mean \pm SD

5.11 . Operational definitions:

A. CKD : According to 2024 KDIGO guideline for CKD , CKD is defined as abnormalities of kidney structure or function, present for a minimum of 3 months, with implications for health . Criteria for chronic kidney disease (either of the following present for a minimum of 3 months)

1. Markers of kidney damage (1 or more):

- a. Albuminuria ($\text{ACR} \geq 30 \text{ mg/g}$ [$\geq 3 \text{ mg/mmol}$])
- b. Urine sediment abnormalities
- c. Persistent hematuria
- d. Electrolyte and other abnormalities due to tubular disorders
- e. Abnormalities detected by histology
- f. Structural abnormalities detected by imaging
- g. History of kidney transplantation

2 . Decreased GFR : $\text{GFR} < 60 \text{ ml/min per } 1.73 \text{ m}^2$ (GFR categories G3a-G5)

B. Diabetes Mellitus: Previously diagnosed Diabetic patients on insulin or oral antidiabetic drug or those having Fasting blood glucose $\geq 7 \text{ mmol/l}$ (126 mg/dl) or Postprandial glucose $\geq 11.1 \text{ mmol/l}$ (200 mg/dl) during OGTT or HbA1C $\geq 6.5\%$.(ADA, 2010)

C. eGFR: The CKD-EPI equation, expressed as a single equation, is:

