- $\text{GFR} = 141 \times \min(\text{Scr}/\kappa, 1)^\alpha \times \max(\text{Scr}/\kappa, 1)^{-1.209} \times 0.993^{\text{Age}} \times 1.018$ [if female] $\times 1.159$ [if black]

Scr is serum creatinine (mg/dL), κ is 0.7 for females and 0.9 for males, α is -0.329 for females and -0.411 for males, min indicates the minimum of Scr/ κ or 1, and max indicates the maximum of Scr/ κ or 1.

D. Diabetic Nephropathy: Diabetic patients with urinary albumin excretion >30 mg/g on at least two occasions three months apart and no other kidney or renal tract disease.(Tuttle et al., 2014)

E. Genital and perineal hygiene : Patient education about genital and perineal hygiene should be taken as a preemptive measure for all the diabetic patients irrespective of the antidiabetic therapy. This should include washing of genital organs followed by urination or defecation, routine hygienic wipes or sprays, women should be advised to wash from front-to-back, uncircumcised males should retract the prepuce before wash, use clean water for washing or mild soap if required, alcohol-based disinfectant should not be used for washing.(Unnikrishnan et al., 2018)

F. Withdrawal criteria

1. A sustained decrease in eGFR to <15 mL/min/1.73 m² or sustained decrease in eGFR \geq 40% compared to baseline over \geq 4 weeks was defined by evidence of \geq 2 consecutive laboratory assessments or need to start dialysis (Bakris et al., 2020)
2. Persistently high potassium level \geq 5.5 mmol/l even after holding Finerenone for 3 days and adjusting other diet and medications.
3. If patient develops diabetic ketoacidosis (DKA) including euglycemic DKA. DKA will be defined as blood glucose >11.1 mmol/L, urine ketone bodies more than 2+ on dipstick testing and a serum bicarbonate level <15 mmol/L.
4. If patient develops symptoms and signs suggestive of Fournier's gangrene (pain, swelling, erythema, foul-smelling discharge or necrosis) in the perineal or genital area.
5. Drug intolerance or patient refusal to continue medication due to adverse effects like dizziness, arthralgia etc.
6. The patient wants to withdraw himself from the study
7. If any participant becomes pregnant during the study period

G. Adverse Events: (AE)

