An AE is defined as any untoward medical occurrence in a clinical trial patient during the study; the event does not necessarily have a causal relationship with that treatment. Therefore, an AE can be any unfavorable and unintended sign (including any clinically significant abnormal laboratory finding), symptoms, or disease, temporally associated with using a medicinal product. The most common adverse event of finerenone is hyperkalemia. Other common adverse events are decreased GFR, hypotension, back pain, dizziness, arthralgias, constipation. The most common adverse events of dapagliflozin is genital mycotic infection. Other adverse events are urinary tract infection, hypotension, hypoglycemia, acute kidney injury, DKA, Fournier's gangrene.

Major adverse events will be defined as any event leading to admission or prolonged admission, withdrawal, or death.

Minor adverse events will be defined as minor if it does not require admission to the hospital or withdrawal of the drug.

Drug intolerance refers to the inability to tolerate the adverse effects of medication at a therapeutic or substantial dose.

H. Treatment Compliance :Compliance to study treatment, calculated as ([overall amount of dose actually taken] / [overall expected amount of dose to be taken]) × 100%, was also assessed (on-treatment + 7 days analysis set, *i.e.*, all patients who received one dose of study treatment and censored at 7 days after treatment discontinuation). The dose taken was based on medication returned by patients to their clinics. Adequate treatment compliance was defined as $\geq 75\%$, and significant noncompliance was defined as $< 50\%$. (Carolina, 2023)

5.12 Data collection instrument: A structured pretested case record form.

5.13 Data collection procedure:

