Baseline evaluation: Patients with chronic kidney disease and type 2 diabetes will be screened consecutively and prospectively by the above inclusion and exclusion criteria to select eligible patients. Eligible patients and their legal relatives will be fully explained the study protocol, their role in the study, and the risk of the study. They will be enrolled in the study after getting written informed consent. Demographic and clinical information will be collected as per the case record form by interviewing the patients, reviewing the medical records, and performing physical examinations. After taking proper history and physical examinations, blood and urine samples will be collected for biochemical analysis. Blood tests will include measurement of Serum Creatinine, Estimated Glomerular Filtration Rate (eGFR), Serum Potassium, Fasting Blood Sugar (FBS), 2-Hour Postprandial Blood Sugar (2HPPBS) and HbA1C. Urine samples will be analyzed for Urine Albumin-Creatinine Ratio (first morning urine) and routine examination (R/E), including albumin, RBC and WBC. If a patient reports symptoms or any biochemical findings suggestive of a Urinary Tract Infection (UTI), a urine culture and sensitivity (C/S) test will be performed. Baseline clinical and laboratory parameters will be recorded in the case record form.

Randomization: Once a participant is enrolled in the study and consents to participate, they will be assigned to a treatment group according to the randomization sequence. Patients will be randomly assigned to either experimental groups or control group with a 1:1 ratio (block size of four). Randomization will be carried out using online software (Research Randomizer Version 4.0 at <https://www.randomizer.org>).

Blinding: The study will be open-label, with both participant and the researcher aware of their treatment allocation.

Treatments: The treatment phase lasted for eight weeks. The experimental group will receive oral dapagliflozin 10 mg plus Finerenone 10 mg daily. While the control group will receive oral dapagliflozin 10 mg daily. All the patients will be advised to follow standard dietary advice (including low salt <5gm/daily, diabetic diet), regular exercise, regular home capillary glucose monitoring & maintain all the standard pharmacological therapies throughout the study, including oral antidiabetic drug/insulin and any other antihypertensive medications (if required).

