Evaluation of patients at 4 weeks: The patients will be followed up at 4 weeks. The physical examinations will be done, and the following parameters will be measured at follow-up: Serum creatinine, eGFR, serum potassium, FBS, 2HPPBS, Urine R/E and Urinary ACR. The patients will be instructed to report immediately in case of any adverse events following consumption of the drugs. If a patient develops symptoms or signs suggestive of genital mycotic infection (itching, erythema, discharge), a culture and sensitivity (C/S) test of vaginal discharge (in female) or penile swab (in male) will be performed. Tolerability will be assessed by employing an adverse event profile (adverse events, serious adverse events). Safety will be evaluated based on the incidence of A/E. The safety population consists of subjects who receive at least one dose of study medication. Necessary action will be taken for any adverse effect complained by participants.

Evaluation of patients at 8 weeks and outcome assessment: All the patients will be evaluated at 8 weeks again. Physical examination will be done. Biochemical parameters will be reassessed, including Serum Creatinine, eGFR, Serum Potassium, FBS, 2HPPBS, urine R/E and urinary ACR. If a patient does not return for a scheduled visit, every effort will be made to contact the patient. If possible, every effort will be made to document patient outcomes in any circumstance. The investigator will enquire about the reason for withdrawal, request that the patient return all unused study medication, and ask that the patient return for a final visit, if applicable, and follow up with the patient regarding any unresolved adverse events

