Appendix

Case record form

Protocol Title: Effect of dapagliflozin compared to dapagliflozin-finenone combination on albuminuria in patients with chronic kidney disease and type 2 diabetes: A randomized controlled trial.

Patient's identification			
1	Patient ID No.		
2	Name of the patient		
3	Contact no:		
4	Address:		
5	Study group: Group 1: Experimental group Group 2: Control group		
Demographic characteristics			
1	Age:years	
2	Sex:	0=Female 1=Male	
3	Place of residence	1=Urban, 0= Rural	
3	Monthly incomeBDT	
Clinical Characteristics			
1	Duration of Diabetes Mellitus years	
2	Duration of Hypertension years	
3	Current medication for DM	1=Insulin 2=Oral Hypoglycemic Agents 3=Both Insulin and Oral Hypoglycemic Agents	
4	Current medication for HTN	1=ACEi, 2=ARB, 3=MRA, 4=Beta blocker, 5=CCB, 6=Diuretics, 7=Others	
Clinical Parameters		Baseline	4 Weeks
1	Height (cm)		
2	Weight (kg)		
3	BMI (kg/m ²)		
4	Systolic BP (mmHg)		
5	Diastolic BP (mmHg)		
Biochemical Parameters		Baseline	4 Weeks
1	Serum Creatinine (mg/dL)		
2	eGFR (mL/min/1.73m ²)		
3	Serum Potassium (mmol/L)		
4	Fasting Blood Sugar (mg/dL)		
5	2-hour Postprandial Blood Sugar (mg/dL)		
6	Urine Albumin-Creatinine Ratio (UACR) (mg/g)		

7	Urine R/E – Albumin:			
8	Urine R/E – RBC:			
9	Urine R/E – WBC:			
	Biochemical Parameters	Baseline	4 Weeks	8 Weeks
10	HbA1C (%)		-	-
11	Urine Culture & Sensitivity (if UTI suspected):			
12	Vaginal discharge/penile swab for C/S (if genital mycotic infection suspected)	-		
13	Urine for ketone bodies (if DKA suspected)			
14	Serum bicarbonate (if DKA suspected)			

Adverse Effect			4 Weeks	8 Weeks
1	Hyperkalemia	1=Yes 2=No		
2	Hypotension	1=Yes 2=No		
3	UTI	1=Yes 2=No		
4	Genital Mycotic Infection	1=Yes 2=No		
5	Hypoglycemia	1=Yes 2=No		
6	Dizziness	1=Yes 2=No		
7	Constipation	1=Yes 2=No		
8	Acute Kidney Injury (AKI)	1=Yes 2=No		
9	Diabetic Ketoacidosis (DKA)	1=Yes 2=No		
10	Fournier's gangrene	1=Yes 2=No		
11	Expired	1=Yes 2=No		
12	Others	1=Yes 2=No		
Outcome		Completed per protocol=1, Withdrawn=2, Lost to follow up =3		

Signature of the researcher:

Signature of the Guide/Co-guide

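### Hyperkalaemia enters the safety comparison as an unblinded yes/no tick with no potassium criterion, although potassium is measured in both arms at every visit

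*Protocol*

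**What the plan says.** - Section 5.11 G (Adverse Events): "The most common adverse event of finerenone is hyperkalemia". The same section counts as an adverse event any unfavourable sign, "including any clinically significant abnormal laboratory finding", with no number attached.
- Section 5.13, evaluation at 4 weeks: "Safety will be evaluated based on the incidence of A/E". The safety population is everyone who took at least one dose.
- Case record form, Adverse Effect table: "Hyperkalemia 1=Yes 2=No", at 4 and 8 weeks, with no cut-off.
- Section 5.13, Blinding: the study is open-label, "with both participant and the researcher aware of their treatment allocation".
- Section 5.7 sets an entry limit for potassium of 4.8 mmol/L or less. Section 5.11 F, item 2, gives a withdrawal rule: "Persistently high potassium level" of 5.5 mmol/L or more despite a 3-day hold of finerenone and other adjustments. No other potassium figures appear.
- Section 4.2, objective 2: "To compare the changes in serum potassium levels between the two groups during the study period". Section 5.10 lists potassium as continuous, mean and SD. Section 5.14 allows median and IQR with a Mann-Whitney test if it is not normal, and gives the chi-square test for categorical variables.
- Serum potassium is measured and recorded in both arms at baseline, week 4 and week 8.

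**The concern.** The incidence of hyperkalaemia is what a reader will look to when weighing the combination against dapagliflozin alone. As written, whether a given potassium value counts as an event is left to a person who knows which patients take the drug associated with it. A borderline value may be ticked in the combination arm and passed over in the control arm, or discounted where it is expected.

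Neither potassium figure in the protocol closes the gap. The entry limit concerns eligibility. The withdrawal figure concerns persistence after holding a drug that the control arm never receives, so it cannot serve as a common event definition as it stands.

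The planned analysis of measured potassium is objective, but it compares centres of distributions. It does not say how many patients reached a high value. Objective 5 (safety and tolerability) and the safety half of the trial's conclusion therefore lean on the tick.

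**Working it through.** **The plan's own figure.** None is given for hyperkalaemia. The only computed figure is the sample size, for UACR: [36×64 + 8×92]/28² × (1.96 + 1.28)² = 3040/784 × 10.498 = 40.7, given as about 40; 40 × 1.10 = 44 per arm. It matters here only because it fixes 44 per arm.

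**Inputs.** From the protocol: 44 per arm, chi-square test, significance at p<0.05. Assumed: on-treatment potassium normal, mean 4.5 mmol/L, SD 0.40 to 0.45, the same in both arms. Two illustrative tick levels are used: 5.5 (the figure in the withdrawal rule) and 5.0 (assumed). Neither is proposed as the definition.

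**Step 1: how much the unstated cut-off matters.** P(K ≥ c) = 1 − Φ((c − 4.5)/SD).

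| SD | P(K ≥ 5.0) | per 44 | P(K ≥ 5.5) | per 44 | ratio |
|---|---|---|---|---|---|
| 0.40 | 0.106 | 4.6 | 0.006 | 0.3 | 17 |
| 0.45 | 0.133 | 5.9 | 0.013 | 0.6 | 10 |

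The choice of cut-off alone moves the expected count 10- to 17-fold.

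**Step 2: false rejection with no true difference.** Each arm's tick count is binomial with n = 44. All pairs of counts were enumerated, and the probability of those with uncorrected chi-square p<0.05 was summed. Grey-zone means 5.0 up to 5.5.

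| How grey-zone values are ticked | SD 0.40 | SD 0.45 |
|---|---|---|
| Same rule in both arms, cut-off 5.0 | 5.9% | 5.6% |
| Same rule in both arms, cut-off 5.5 | 0.0% | 0.3% |
| All in combination, three quarters in control | 7.9% | 8.0% |
| All in combination, half in control | 15% | 17% |
| Half in combination, none in control | 18% | 26% |
| All in combination, none in control (extreme) | 60% | 68% |

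Using Fisher's exact test in the extreme case still gives 26% and 39%.

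**Step 3: what the mean comparison adds.** With 44 per arm and a true shift of 0.2 mmol/L, a two-sided t-test has power 64% (SD 0.40) and 54% (SD 0.45). A count at 5.5 has 1% and 5%. For a shift of 0.3 the figures are 94% and 87%, against 8% and 17%. The mean comparison is the more sensitive test of whether potassium rises. The count answers a different question: how many patients reach a high level.

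**The case against.** The strongest reply is that nothing is lost. Potassium is recorded on the same form at each visit, so every tick can be checked against a laboratory value, and a statistical analysis plan that is not shown might add a threshold count. This is right about the data and explains why the repair is cheap. It does not remove the point, because the protocol itself fixes the recording item, the basis of the safety evaluation and the test. It also sets a numeric event definition where it chooses to: diabetic ketoacidosis is defined by glucose, ketones and bicarbonate in 5.11 F.

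Four stronger readings are tempting but not supported.

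- A reader might infer that all adverse events will be pooled into one variable, since 5.10 lists them as "Present / Absent", and that a hyperkalaemia excess would be diluted. The case record form gives each named event its own row and 5.13 asks for an adverse event profile, so the entry reads more naturally as the coding of each event. No any-event test is stated.
- A reader might infer that the planned potassium comparison is no safeguard. Objective 2 is an objective between-arm comparison. If the arms were truly alike, it would tend to contradict a false excess of ticks (Step 3). What it cannot supply is a valid incidence.
- A reader might take 60 to 68% as the expected error. It requires every grey-zone value to be ticked in one arm and none in the other. Nothing in the documents shows that this, or any other pattern, will occur.
- A reader might lift existing figures into event definitions. The 5.5 mmol/L figure belongs to a persistent-value withdrawal rule, the 40% eGFR fall to a sustained one, and systolic pressure below 90 mmHg to screening. The protocol does not offer any of them as the definition of an event.

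**Conclusion.** The point holds. The hyperkalaemia incidence comparison rests on an unblinded judgement with no stated criterion, while an objective measurement taken in both arms is not used to classify the event. The comparison is open to ascertainment bias.

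The documents do not settle the size or direction. On the assumed potassium distribution, false rejection is about 15 to 26% when half the grey-zone values are treated differently between arms, about 8% when a quarter are, and 60 to 68% at the extreme. With one common rule it is at most 6%. These are illustrations, not predictions.

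The primary UACR analysis is untouched. The defect bears on objective 5 and on the safety conclusion, and is worth correcting before data are reviewed.

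**What to change.** In 5.10 and 5.14, define the hyperkalaemia outcome from recorded post-baseline potassium by a single laboratory threshold, chosen by the investigators before data review and applied identically in both arms. Report number and percent per arm, with the difference and its 95% CI, in the safety population of 5.13, alongside the objective 2 comparison. Keep the case record form tick as a descriptive item.

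The choice of threshold is left to the investigators. Its relation to the withdrawal figure in 5.11 F, item 2, should be stated so that the two passages are reconciled. Where the investigators hold a numeric definition of acute kidney injury or hypotension, those events should be derived in the same way from recorded creatinine or eGFR and blood pressure.

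The cost is a few sentences. All values are already collected, so no test, visit or patient is added. The downside is that counts will be small and the interval wide: the change removes a source of bias, not the imprecision of 44 patients per arm.

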Materials and Methods: This open-label randomized controlled trial will be conducted in the Department of Nephrology of Chittagong Medical College Hospital, Chattogram, Bangladesh including 88 patients with chronic kidney disease and type 2 diabetes. Participants will be randomized into one of two study groups. The experimental group will be treated with dapagliflozin 10 mg plus finerenone 10 mg once daily for eight weeks. The control group will receive dapagliflozin 10 mg once daily for the same duration. The primary outcome measure will be the change in UACR, while the other variables will include serum creatinine, eGFR, serum potassium. Adverse events and safety measures will also be recorded. The primary analysis will follow either an intention-to-treat or a perprotocol approach and will be performed using SPSS version 27.

Conclusion: This study will elucidate the efficacy and safety of dapagliflozin - finerenone combination in a Bangladeshi cohort, potentially guiding strategies to mitigate albuminuria in T2DM.

PART-D

1. Introduction:

Chronic kidney disease is a common and serious complication in individuals with type 2 diabetes, contributing significantly to morbidity and mortality. It progresses silently and is frequently associated with increased cardiovascular risks and reduced renal function (Navaneethan et al., 2025; Hansrivijit et al., 2025).

The global prevalence of chronic kidney disease (CKD) among patients with type 2 diabetes mellitus (T2DM) is a growing concern, with approximately 27% of diabetic individuals affected worldwide according to a recent meta-analysis (Fenta et al., 2023). Regional studies further highlight this burden; in the United States, CKD prevalence among T2DM patients rose to 1.28% by 2018 (Feng et al., 2021). In Ethiopia, prevalence estimates vary significantly, reaching 31.5% in South Wollo (Adem et al., 2024) and 14.3% in Northwest regions (Alemu et al., 2020). Recent studies from Bangladesh according to Mahbub et al. (2024), the prevalence of CKD among T2DM patients in selected hospitals in Dhaka was found to be 34.5%, highlighting a critical public health issue. This aligns with global estimates but emphasizes regional variation due to socioeconomic, environmental, and healthcare access factors. These disparities reflect underlying differences in healthcare access, screening practices, and comorbid conditions, underscoring the need for targeted interventions and enhanced surveillance globally.

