In every visit, for blood test, blood will be collected from accessible vein with proper aseptic precaution and patient remained at least 8 hours overnight fasting before blood collection and blood was collected into red topped vacutainer. After collection of 10 mL blood, it will be allowed to clot by leaving it undisturbed at room temperature for 10-15 minutes and will removed the clot by centrifuging at 3000rpm for 10 minutes for serum. Serum creatinine concentration will be measured by buffer kinetic jaffe reaction using a SIEMENS dimension EXL200 analyzer while eGFR will be measured by CKD-EPI formula. The urinary albumin concentration was determined using a nephelometry method by BN pro-spec analyzer while urinary creatinine concentration was measured by endpoint spectrophotometric method with an alkaline picrate solution using a SIEMENS dimension EXL200 analyzer. UACR will be calculated by dividing the concentration of urinary albumin by the concentration of urinary creatinine. All the investigations will be performed in an ISO certified laboratory.

5.14. Data analysis:

Data will be recorded in the form of an Excel worksheet. After completion of data collection, data will be analyzed using the Statistical Package for Social Sciences (SPSS) version 27.0 (IBM Corp., Armonk, NY, USA). The continuous variables will be presented by measures of central tendency and measures of dispersion. For the normally distributed data, mean \pm standard deviation will be used, and for non-parametric data, median and Interquartile range (IQR) will be presented. On the other hand, we would present the categorical variables as frequency distribution. Between groups, comparisons of independent variables will be performed by independent t-test and Mann-Whitney U-test for normally and not-normally distributed variables respectively. Within patients, comparison will be performed by paired t-test or Wilcoxon Signed Rank Test, as appropriate. The Chi-square test will investigate the differences in categorical variables between two groups. Repeated measures ANOVA will be performed to compare mean values across multiple time points within the same group. Where appropriate, post-hoc analysis with Bonferroni correction will be conducted to identify specific time points with significant difference. A p-value <0.05 will be considered statistically significant.

[figure not shown]

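### Section 5.14 tests the change in UACR without baseline adjustment, log scale or named effect measure, and the scale of the change is not fixed; a log-scale ANCOVA would settle all of these at no cost

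*Protocol*

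**What the plan says.** The Summary (Part C) states: "The primary outcome measure will be the change in UACR". Objective 1 in section 4.2 is "To compare the change in urinary albumin-to-creatinine ratio (UACR) from baseline to the end of the study between" the two groups. Neither says whether the change is absolute, percent or logarithmic.

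Section 5.14 does not treat the primary outcome separately. Its rule for continuous variables is "Between groups, comparisons of independent variables will be performed by independent t-test and Mann-Whitney U-test" "for normally and not-normally distributed variables respectively". The only multi-visit model is confined to a single arm: "Repeated measures ANOVA will be performed to compare mean values across multiple time points within the same group". It therefore cannot answer objective 1. The threshold is "A p-value <0.05 will be considered statistically significant".

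Other sections point to different scales:

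- Section 5.10 lists UACR as a continuous variable in mg/g, expressed as mean ± SD.
- Section 5.9 defines its inputs as percent change from baseline in UACR, 36% in the experimental arm and 8% in the control arm.
- Objective 4 is relative: "To evaluate the proportion of patients achieving a clinically significant reduction in albuminuria", with a fall of 30% or more as the example.
- Section 5.14 allows median and IQR for non-normal data, which differs from the mean ± SD listed for UACR in 5.10.

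Section 5.7 admits patients with UACR of 30 mg/g or more and sets no upper limit.

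**The concern.** A variable with a floor and no ceiling will be right-skewed. On the mg/g scale a proportional drug effect is weighted by baseline: a 36% fall is 720 mg/g for a patient starting at 2,000 mg/g and 36 mg/g for one starting at 100 mg/g, a factor of 20. A comparison in mg/g is then driven by the few patients with the highest baseline, and a difference in mg/g cannot be read against the 36% v 8% on which the trial was planned.

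When the normality check fails, the primary result becomes a Mann-Whitney p-value. The protocol names no estimate or interval to go with it, so the reader would not learn by what percentage the combination lowers UACR relative to dapagliflozin alone.

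The protocol also leaves open which version of the change is tested. In an open-label trial (5.13, Blinding), a choice that can move power by some 20 points should not be left until the data are visible.

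**Working it through.** **The plan's own figure.** Section 5.9 uses the two-proportion formula:

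n = [36 × 64 + 8 × 92] / 28² × (1.96 + 1.28)² = 3,040 / 784 × 10.4976 = 40.70.

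The protocol shows 40 and adds 10%, giving 44 per arm and 88 in total. The figure reproduces apart from rounding down. It rests on a formula for proportions, which is not the test in 5.14; that is a separate matter. The 40 evaluable patients per arm are carried forward here.

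**The planning effect on the log scale.** Falls of 36% and 8% leave 0.64 and 0.92 of baseline. The ratio is 0.64 / 0.92 = 0.696, and the log difference is δ = ln(0.92 / 0.64) = 0.363. For a t-test on log change, n per arm is about 2 (σ/δ)² (1.96 + 1.28)². With σ = 0.5 this is 2 × (0.5 / 0.363)² × 10.4976 ≈ 40, so 40 per arm gives 90% power only if the SD of log change is about 0.5. At SD 0.6 and 0.7, power is 77% and 64%.

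**Power of the stated rule, by scale.** This was simulated.

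- From the protocol: 40 per arm, changes of −36% and −8%, two-sided 0.05, and the t-test or Mann-Whitney choice.
- Assumed, because the protocol gives no figures: log-normal UACR, median baseline 300 mg/g, baseline log SD 0.9 and 1.2, slope of follow-up on baseline 0.85 on the log scale, residual log SD 0.5, 0.6 and 0.7, and Shapiro-Wilk as the normality check.
- 1,500 runs per scenario, with a Monte Carlo error of about 1.3 points.

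| Residual log SD | Rule on change in mg/g | Rule on percent change | ANCOVA of log UACR |
|---|---|---|---|
| 0.5 | 62–68% | 85–87% | 89% |
| 0.6 | 49–55% | 69–71% | 75–76% |
| 0.7 | 42–44% | 57–58% | 62% |

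A second run of the same scenarios gave 59–66% / 48–54% / 41–45% for the rule on change in mg/g, and 87–88% / 76–77% / 64–65% for log ANCOVA. Subtracting the ends of these ranges puts the mg/g loss between 18 and 29 points across both runs, or about 20 to 28 in round terms. For percent change the loss is about 3 to 7 points.

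**A different set of assumptions.** Here log UACR has SD 0.8 to 1.2 at both visits and a baseline to week-8 correlation of 0.6 to 0.9.

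- Rule on change in mg/g: loss of 8 to 27 points. For example, at SD 1.0 and correlation 0.8 it is 51% v 78%. The 8 is at SD 0.8 and correlation 0.9, 92% v about 100%.
- Mann-Whitney on percent change: loss of 1 to 10 points. At SD 1.0 and correlation 0.8 it is 71% v 78%.

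**What the normality rule does.** For change in mg/g it selected Mann-Whitney in 99–100% of simulated trials, and its power was the same as that of Mann-Whitney alone. Choosing the test from the data therefore does little harm in itself. What matters is that the outcome is predictable: a rank test with no named estimate.

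**Where the loss comes from.** In the first set of scenarios log ANCOVA beat a plain t-test on log change by about 1 to 3 points. In the second set the gain was 0 to 7 points (61% v 68% at SD 0.8 and correlation 0.6). Most of the loss therefore comes from the scale, and a smaller part from the missing covariate.

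**The case against.** The strongest reply is that the protocol never says the test will be run on mg/g. The only place where the change is defined is 5.9, as percent change, and objective 4 is also relative. A reader may fairly apply 5.14 to percent change, and then little power is lost. This stands, and it is why the large loss can only be stated conditionally.

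Four stronger readings are tempting, and the protocol does not support them:

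- *That UACR will be analysed untransformed.* This is inferred from the mg/g listing in 5.10 and the absence of any transformation; it is not stated.
- *That baseline UACR is ignored.* A change score subtracts baseline, so it is partly used. What is missing is adjustment for it.
- *That no usable effect estimate is possible.* A t-test gives a mean difference with an interval, a Hodges-Lehmann shift can accompany Mann-Whitney, and objective 4 gives responder proportions. The accurate statement is that 5.14 names no effect measure.
- *That power would be judged on raw week-8 values.* Power is much lower there, but objective 1 compares change from baseline.

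It is also fair to say that Mann-Whitney on change is a valid test, so log ANCOVA improves efficiency and interpretation and does not rescue an invalid analysis. Section 5.14 already allows median and IQR for skewed data, so the presentation point is only a mismatch with 5.10.

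A separate analysis plan could add a scale and a model. But 5.14 already names the tests and how to choose between them, so a different primary model there would have to depart from the protocol.

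**Conclusion.** The point holds in this form: 5.14 fixes an unadjusted test chosen by normality, with no log scale and no named effect measure, while the protocol points to two different scales for the change. With an unbounded UACR the result will almost always be a rank p-value with no specified effect on the scale used for planning.

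The cost in power depends on the scale. Against log ANCOVA with 40 per arm it is about 20 to 28 points for change in mg/g and about 3 to 7 points for percent change, at residual log SD 0.5 to 0.7. All SDs, the slope and the median baseline are assumptions, so the direction is firmer than the exact figures. A reader might infer that the trial as written throws away a large part of its power. That is established only if change in mg/g is tested, which the protocol does not settle.

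This is a worthwhile improvement to make before any outcome data are examined. It does not show that the planned test is invalid.

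**What to change.** In 5.14, add a sentence for the primary outcome: *Primary analysis: ANCOVA of log UACR at week 8 with treatment group and baseline log UACR; the result is the ratio of geometric means, reported as a percent difference with 95% CI and two-sided p-value.* Keep Mann-Whitney on percent change as a named sensitivity analysis.

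In 5.10, replace mean ± SD for UACR by geometric mean or median (IQR), so that it agrees with 5.14.

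This fixes the scale, the adjustment and the effect measure together, and puts the result on the same relative footing as 5.9 and objective 4. It costs only the wording: UACR is already measured at baseline and at 8 weeks, the model runs in SPSS, and no patient, visit or assay is added.
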